## 7.5 Pre-Study Assessments

1. Consent obtained prior to study assessments
2. Complete medical history and complete physical examination
3. ECOG Performance status
4. Tumor Measurement
5. Electrocardiogram
6. Toxicity Evaluation per NCI CTCAEv4.03 for notation of baseline toxicity
7. Concomitant medications
8. Tumor tissue collection (archival)
9. Laboratory evaluations:
  - Hematology
  - Complete Metabolic Panel (CMP) + Magnesium (Mg)
  - Alpha-gal test (Southeastern US sites)
  - Serum pregnancy test in women of childbearing potential (Note: pregnancy test to be done within 72 hours of day 1 of treatment)

## 7.6 Treatment Assessments

Study visits should be performed with +/-3 days of the scheduled assessment unless otherwise specified.

### 7.6.1 D1 of Cycle 1

1. Focused medical history and complete physical examination
2. ECOG Performance status
3. Toxicity Evaluation
4. Concomitant medications
5. Patient diary
6. Laboratory evaluations (do not repeat if performed within last 72 hrs)
  - Hematology
  - Complete Metabolic Panel (CMP) + Magnesium
  - CEA
  - Blood sample for correlates
7. Administer Study Medications (See section 5.2 for details on treatment dosage and administration)

### 7.6.2 D8 of Cycle 1

1. Toxicity Evaluation
2. Concomitant medications
3. Laboratory evaluations)
  - Magnesium (Mg) and potassium
4. Administer Study Medications (See section 5.2 for details on treatment dosage and administration)

### 7.6.3 D15 of Cycle 1

1. Focused medical history and physical examination

2. ECOG Performance status
3. Toxicity Evaluation
4. Concomitant medications
5. Laboratory evaluations
  - Hematology
  - Complete Metabolic Panel (CMP) + Magnesium
6. Administer Study Medications (See section 5.2 for details on treatment dosage and administration)

#### **7.6.4 D22 of Cycle 1**

1. Toxicity Evaluation
2. Concomitant medications
3. Tumor biopsy (optional)
4. Laboratory evaluations)
  - Magnesium (Mg) and potassium
  - Blood sample for correlates
5. Administer Study Medications (See section 5.2 for details on treatment dosage and administration)

#### **7.6.5 D1 of Cycle 2**

1. Focused medical history and complete physical examination
2. ECOG Performance status
3. Toxicity Evaluation
4. Concomitant medications
5. Patient diary
6. Laboratory evaluations)
  - Hematology
  - Complete Metabolic Panel (CMP) + Magnesium
  - CEA
  - Blood sample for correlates
7. Administer Study Medications (See section 5.2 for details on treatment dosage and administration)

#### **7.6.6 D8 of Cycle 2**

1. Laboratory evaluations)
  - Magnesium and potassium
2. Administer Study Medications (See section 5.2 for details on treatment dosage and administration)

#### **7.6.7 D15 of Cycle 2**

1. Focused medical history and physical examination
2. ECOG Performance status
3. Toxicity Evaluation
4. Concomitant medications
5. Laboratory evaluations

- Hematology
- Complete Metabolic Panel (CMP) + Magnesium
- 6. Administer Study Medications (See section 5.2 for details on treatment dosage and administration)

#### 7.6.8 D22 of Cycle 2

1. Laboratory evaluations
  - Magnesium and potassium
  - Blood sample for correlates
2. Administer Study Medications (See section 5.2 for details on treatment dosage and administration)

#### 7.6.9 D1 of Cycles 3-N

1. Focused medical history and physical examination
2. ECOG Performance status
3. Tumor measurement (every 8 weeks per footnote #4 of Time & Events table)
4. Toxicity Evaluation
5. Concomitant medications
6. Patient diary
7. Laboratory evaluations)
  - Hematology
  - Complete Metabolic Panel (CMP) + Magnesium
  - CEA
  - Blood sample for correlates (only on cycles 4, 6, 8, etc)
8. Administer Study Medications (See section 5.2 for details on treatment dosage and administration)

#### 7.6.10 D8 of Cycles 3-N

1. Laboratory evaluations
  - Magnesium (Mg) and potassium
2. Administer Study Medications (See section 5.2 for details on treatment dosage and administration)

#### 7.6.11 D15 of Cycles 3-N

1. Toxicity Evaluation
2. Concomitant medications
3. Laboratory evaluations
  - Magnesium and potassium
4. Administer Study Medications (See section 5.2 for details on treatment dosage and administration)

#### 7.6.12 D22 of Cycles 3-N

1. Laboratory evaluations
  - Magnesium and potassium

- Blood sample for correlatives (only on cycle 4, 6, 8, etc)
- 2. Administer Study Medications (See section 5.2 for details on treatment dosage and administration)

## 7.7 Post-Treatment/Follow-up Assessments

### 7.7.1 End of treatment

A subject who is being withdrawn for disease progression or for other reasons (e.g. unacceptable toxicity, etc.) should complete an end of treatment visit.

1. Focused medical history and complete physical examination
2. ECOG Performance status
3. Toxicity Evaluation
4. Concomitant medications
5. Patient diary
6. Laboratory evaluations (do not repeat if performed within last 72 hrs)
  - Hematology
  - Complete Metabolic Panel (CMP) + Magnesium (\*\*If severe hypomagnesemia or hypokalemia is detected at the end of treatment visit, then follow until resolution per institutional standard)
  - CEA
  - Blood sample for correlatives

### 7.7.2 Day 56 follow-up (+/- 7 days)

1. Toxicity Evaluation
2. Concomitant medications
3. Laboratory evaluations
  - Potassium + Magnesium

### 7.7.3 Long-term follow up

Subjects should be followed per standard of care after withdrawal from study treatment. Subsequent follow-up visits, defined as every 90 days thereafter (+/- 15 days) for up to 3 years or until death (whichever is first) may be conducted via telephone and/or via clinic visit. These visits will be limited to history of any subsequent cancer treatments, an assessment of any SAEs considered to be possibly or probably related to study treatment until resolution, and survival status.

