#### 3.2 Secondary Endpoints

- 3.2.1 Objective response, defined as complete or partial response based on RECIST 1.1 criteria.
- 3.2.2 Overall survival (OS), defined as time from first dose of study drug to death from any cause.
- 3.2.3 Progression-free survival (PFS), defined as time from first dose of study drug to progression or death from any cause.
- 3.2.4 Toxicity assessed per NCI CTCAE v4.03 starting on day 1 of study treatment.

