### **5.7 Duration of Follow Up**

All patients will be followed for up to 3 years, or until death, whichever occurs first after removal from study treatment for determination of study endpoints. Patients removed from study treatment for unacceptable AEs will be followed for resolution or stabilization of the adverse event(s). All patients (including those withdrawn for AEs) should be followed after removal from study treatment as stipulated in the protocol.

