### **9.3 Data Analysis Plans**

DCRs and ORRs for both cohorts will be reported with their 95% confidence intervals. PFS and OS will be estimated using the Kaplan-Meier method. Toxicity and safety information will be reported in a descriptive manner in the form of frequency tables. Hypothesis generating [REDACTED], in the form of logistic and Cox regression, designed to investigate potential associations between the outcomes of response rates, such as DCR and ORR, and of PFS and OS, between selected tumor mutations and pharmaco-dynamic biomarkers of interest will be performed when appropriate sample size considerations allow.

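### No visit after treatment stops collects a progression date, although PFS is not limited to time on treatment, so Kaplan-Meier PFS is at risk of being too long

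*Combined protocol and SAP*

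**What the plan says.** **Endpoint and analysis.** Section 3.2.3: "Progression-free survival (PFS), defined as time from first dose of study drug to progression or death from any cause". Section 9.3: "PFS and OS will be estimated using the Kaplan-Meier method". Neither section says what happens to a patient who stops treatment without progression or starts another therapy.

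**Stopping without progression.** Section 5.6 allows it for adverse events, intercurrent illness, the patient's decision or the investigator's judgment. No expected share is given.

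**Visits after the stop.**
- 7.7.1 (end of treatment) applies to these patients too. It lists history, examination, performance status, toxicity, medications, diary and laboratory work.
- 7.7.2 (Day 56) lists toxicity, medications, potassium and magnesium.
- 7.7.3: "Subjects should be followed per standard of care after withdrawal from study treatment". The contacts, which may be by telephone, are scheduled as follows: "Subsequent follow-up visits, defined as every 90 days thereafter (+/- 15 days) for up to 3 years or until death". On content: "These visits will be limited to history of any subsequent cancer treatments", then treatment-related SAEs "until resolution, and survival status".

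**Text pointing the other way.** Section 7.1.7 and footnote 4 of 7.4 set imaging every 8 weeks after baseline, with no stated end. Section 5.7 provides follow-up to 3 years or death, "whichever occurs first after removal from study treatment for determination of study endpoints". It then refers to follow-up as the protocol stipulates, which leads back to 7.7.3. In the visit lists, post-baseline tumour measurement appears only at Day 1 of cycle 3 onward (7.6.9), while on treatment.

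**The concern.** A Kaplan-Meier PFS curve needs, for each patient, an event date or a date to which the patient is known to be progression-free. Off treatment the plan collects neither from imaging. The analyst must then choose between censoring at the last scan, waiting for death, and counting new therapy as an event. These give different curves from the same patients, and the choice would be made after the data are seen. Sites may also differ: one may read 7.1.7 as continuing the scans, another may collect only what 7.7.3 lists.

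At stake is the credibility of a secondary endpoint in two small uncontrolled cohorts. Two of the three choices can only leave PFS unbiased or make it too long, unless the progression hazard falls after stopping.

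**Working it through.** **1. What is observable after a stop without progression**

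| Item | Collected? | Source |
|---|---|---|
| Death | Yes, up to 3 years | 7.7.3 |
| Start of new cancer therapy | Yes | 7.7.3 |
| Date or basis of progression | Not in any listed visit | 7.7.1 to 7.7.3 |

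The tumour-measurement row of the 7.4 table is damaged in the text available and is not relied on.

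**2. The plan's own figures.** There is no PFS target, event count or dropout figure. The usable inputs are the 4-month disease control rates in 9.2. For Cohort A (continue at 6 or more of 12, succeed at 15 or more of 26), P(success) = sum over x from 6 to 12 of b(x; 12, p) × P(Bin(14, p) ≥ 15 − x). This is 0.0469 at p = 0.40 and 0.8086 at p = 0.65. The same form for Cohort B (4 of 10, 11 of 21) gives 0.0496 at 0.33 and 0.8117 at 0.60. The designs reproduce, and PFS follow-up does not affect N.

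**3. Censoring at treatment stop, at the planned alternatives.** Assumptions not in the documents: the alternative rates (65%, 60%) stand for 4-month PFS; progression on treatment has constant hazard λ; stops without progression occur at constant rate μ; the hazard becomes kλ afterwards. Censoring at stop approximates censoring at the last scan.

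- λ = −ln(0.65)/4 = 0.1077 per month (A); −ln(0.60)/4 = 0.1277 (B)
- Share stopping without progression: f = μ/(λ + μ)
- Kaplan-Meier with censoring estimates exp(−λt) whatever k is: 0.650 and 0.600 at 4 months, medians ln 2/λ = 6.4 and 5.4 months
- True PFS: S(t) = exp(−(λ+μ)t) + [μ/(λ+μ−kλ)] × [exp(−kλt) − exp(−(λ+μ)t)]

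Cohort A, f = 0.30, k = 3: μ = 0.1077 × 0.3/0.7 = 0.0462. S(4) = 0.540 + [0.0462/(0.1539 − 0.3231)] × (0.275 − 0.540) = 0.613. Overstatement is 0.650 − 0.613 = 3.7 points.

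True 4-month PFS (overstatement in points):

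| Cohort, f | k = 1 | k = 2 | k = 3 |
|---|---|---|---|
| A, 10% | 0.650 (0) | 0.644 (0.6) | 0.640 (1.0) |
| A, 20% | 0.650 (0) | 0.637 (1.3) | 0.628 (2.2) |
| A, 30% | 0.650 (0) | 0.629 (2.1) | 0.613 (3.7) |
| B, 10% | 0.600 (0) | 0.593 (0.7) | 0.588 (1.2) |
| B, 20% | 0.600 (0) | 0.584 (1.6) | 0.573 (2.7) |
| B, 30% | 0.600 (0) | 0.574 (2.6) | 0.555 (4.5) |

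In the 30%, k = 3 corner the true median is 5.5 against 6.4 reported (A), and 4.6 against 5.4 (B).

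**4. A shorter PFS with earlier stopping.** Assume a median of 4.0 months, which lies between the medians implied by the nulls (3.0 and 2.5) and by the alternatives. A share f is given a stop time uniform over months 0 to 4. Reported 4-month PFS is 0.500; true S(4) = (1 − f) × 0.5 + f × (0.5 − 2^(−k))/[(k − 1) ln 2].

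- f = 0.1, k = 1.5: 0.492, overstated by 0.8 points
- f = 0.2, k = 2: 0.472, overstated by 2.8 points
- f = 0.3, k = 3: 0.431, overstated by 6.9 points (median 3.4 against 4.0)

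Some of the share f progress before their stop time, so those who actually stop number f × 0.5/ln 2, or about 7%, 14% and 22%.

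**5. Death as the only off-treatment event.** Keep the step 3 model and assume a median of 6 months from progression to death. The reported median becomes 6.6 to 7.5 months in A (truth 5.5 to 6.4) and 5.6 to 6.4 in B (truth 4.6 to 5.4). With k = 1 and f = 30% in A it is 7.5 against 6.4, so this bias needs no change in hazard.

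**6. Month 4.** The share stopping without progression before month 4 is f × [1 − exp(−4λ/(1 − f))]: 4% to 14% in A and 4% to 16% in B for f from 10% to 30%.

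**The case against.** Several points count against a broader claim.

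- A reader might infer that these patients have no PFS event date at all. That is wrong: death is a PFS event and survival status is collected. Only the progression date is missing.
- A reader might infer that PFS is informatively censored. The documents do not show this. They state no censoring rule, no stop rate and no link between stopping and prognosis, and with an unchanged hazard the censoring bias is zero. Waiting for death is late ascertainment, not informative censoring.
- The 8-weekly schedule in 7.1.7 and footnote 4 has no end date, and 5.8 asks for a final evaluation and record abstraction from patients leaving the study. So the gap is partly a conflict between sections. However, 5.8 concerns study withdrawal, not stopping treatment alone, and 7.7.3 restricts content expressly.
- PFS is secondary, untested and descriptive. For a rate of 50% the approximate 95% half-width is 1.96 × √(0.25/26) = 19 points in A and 1.96 × √(0.25/21) = 21 points in B, well above the bias computed. That limits the severity, but imprecision does not cancel a one-directional error.
- A reader might infer that the primary endpoint is missing for everyone who stops before month 4. The documents do not settle this. Section 3.1 takes status 4 months after first dose, where a scan could be missing. Sections 5.1 and 9.2 speak of disease control on the regimen, under which an early stop may simply be a non-success. A death before month 4, or a stop just after the week-16 scan, also leaves a known status.

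**Conclusion.** The point holds as a risk of bias in PFS and as an unreconciled conflict between 7.7.3 and sections 7.1.7, 7.4 (footnote 4) and 5.7. It is more than missing detail, because 7.7.3 restricts what may be collected and so loses progression dates that standard care would often produce.

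Under censoring, the overstatement of 4-month PFS is 0 to about 4-5 points at the planned alternatives and up to about 7 points in the shorter-PFS corner case (30%, hazard tripled). If death is the only off-treatment event, median PFS is too long even at a hazard ratio of 1. All sizes rest on assumed stop rates, hazard ratios, exponential times and, for the death case, 6 months' median survival after progression. OS is unaffected. The change is worth making, but it does not threaten the trial's main decision rule.

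**What to change.** 1. In 7.7.3, add to the collected items the date and basis of progression from standard-of-care imaging, until progression, new anticancer therapy or death.
2. Reconcile 7.1.7 and footnote 4 of 7.4 with 7.7.3 by stating whether the 8-weekly schedule ends when treatment stops.
3. In 9.3, state one PFS event and censoring rule covering a stop without progression and the start of new therapy. Add a sensitivity analysis that counts either as an event.
4. Separately, reconcile 3.1 with 5.1 and 9.2 before deciding whether an off-treatment scan may count toward month-4 disease control. Until then such scans should not feed the two-stage counts, because they could change a go/no-go result.

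Cost: a small addition to the eCRF, a few sentences, and some extra data entry and scan reading. Patients are already contacted every 90 days, no extra scan is mandated by item 1, and N stays at 26 and 21. The downside is that off-treatment scans are less regularly timed, so some progressions will be dated late.

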## 7.8 Handling of Biospecimens Collected for Correlative Research

Biospecimens collected for this study will be stored in the Lineberger Comprehensive Cancer Center (LCCC) Tissue Procurement Facility (TPF), or if needed, in a secure off-site storage facility. All biospecimen samples will be obtained in accordance with procedures outlined in the LCCC 1717 Study Laboratory Manual and stored in containers with controlled access. Each sample

will be assigned a unique code number and no identifiable personal health information (PHI) will be on the specimen label. Information about the patient's disease will be linked to the specimens stored in the repository database. TPF-associated research staff, LCCC Bioinformatics staff who support the TPF database and the LCCC Data Warehouse, and researchers with IRB-approval for access to PHI for each subject in this study will be able to link specimens to relevant medical information. Some results from laboratory analyses that occurred during the patient's participation in the clinical study may also be included. This information may be important for understanding how the patient's cancer developed and responded to treatment.

**Storage Time:**

- The biospecimen will be used first and foremost for research purposes outlined within the confines of this protocol. Samples will be discarded/destroyed after relevant data are collected for this study, unless consent was obtained from the patient to use tissue for other research purposes (e.g., TPF consent form was signed by the patient). In this circumstance, there is no time limit on how long biospecimens may be stored.
  - The investigator must agree to abide by policies and procedures of the TPF facility and sign a letter of research agreement for ethical and appropriate conduct of their research that utilizes specimens obtained from the TPF facility (e.g., Use of leftover specimens will require a protocol outlining the research plan for biospecimen use).

**Compliance Statement**

Biospecimen collection for this study will be conducted in full accordance to all applicable University of North Carolina (UNC) Research Policies and Procedures and all applicable Federal and state laws and regulations including 45 CFR 46, and the Health Insurance Portability and Accountability Act (HIPAA) Privacy Rule. Any episode of noncompliance will be documented.

The investigators will perform the study in accordance with this protocol, will obtain consent and assent (unless a waiver is granted), and will report unexpected problems in accordance with The UNC IRB Policies and Procedures and all federal requirements. Collection, recording, and reporting of data will be accurate and will ensure the privacy, health, and welfare of research subjects during and after the study.

**7.9 Assessment of Safety**

Any patient who receives at least one dose of study therapy on this protocol will be evaluable for toxicity. Each patient will be assessed periodically for the development of any toxicity according to the Time and Events table. Toxicity will be assessed according to the NCI CTCAEv4.0.3.

## 7.10 Assessment of Efficacy

### 7.10.1 Assessment of Disease-Tumor Measurement Based on RECIST 1.1

See the international criteria proposed by the Response Evaluation Criteria in Solid Tumors (RECIST) Committee, version 1.1 (Eur J Cancer 45;2009:228-247) for additional details on RECIST1.1.

Measurable disease will be defined as the presence of at least one measurable lesion that can be accurately measured in at least one dimension with the longest diameter a minimum size of:

- $\geq 10$ mm by CT scan (CT scan slice thickness no greater than 5 mm)
- 10mm caliper measurement by clinical exam (lesions which cannot be accurately measured with calipers should be recorded as non-measurable).
- 20 mm by chest x-ray.

For malignant lymph nodes to be considered pathologically enlarged and measurable, a lymph node must be  $\geq 15$ mm in short axis when assessed by CT scan (CT scan slice thickness recommended to be no greater than 5mm). At baseline and in follow-up, only the short axis will be measured and followed.

All other lesions, including small lesions (longest diameter  $<10$ mm or pathological lymph nodes with  $\geq 10$  to  $<15$  mm short axis) as well as truly non-measurable lesions, will be considered non-measurable. Lesions considered truly non-measurable include: leptomeningeal disease; ascites; pleural/pericardial effusion; inflammatory breast disease; lymphangitic involvement of skin or lung, abdominal masses/abdominal organomegaly identified by physical exam that is not measurable by reproducible imaging techniques.

All measurements should be recorded in metric notation, using calipers if clinically assessed. All baseline evaluations should be performed as close as possible to the treatment start and never more than 4 weeks before the beginning of the treatment. The same method of assessment and the same technique should be used to characterize each identified and reported lesion at baseline and during follow-up. Imaging based evaluation should always be done rather than clinical examination unless the lesion(s) being followed cannot be imaged but are assessable by clinical exam. Clinical lesions will only be considered measurable when they are superficial and  $\geq 10$  mm diameter as assessed using calipers (e.g. skin nodules). For the case of skin lesions, documentation by color photography including a ruler to estimate the size of the lesions is recommended.

### 7.10.2 Baseline Documentation of Target and Non-Target Lesions

All measurable lesions up to a maximum of 5 lesions total (and a maximum of two lesions per organ) representative of all involved organs should be identified as target lesions and will be recorded and measured at baseline.

Target lesions should be selected on the basis of their size (lesions with the longer diameter), be representative of all involved organs, but in addition should be those that lend themselves to reproducible repeated measurements.

A sum of the diameters (longest for non-nodal lesions, short axis for nodal lesions) for all target lesions will be calculated and reported as the baseline sum diameters. If lymph nodes are to be included in the sum, only the short axis is added into the sum. The baseline sum diameters will be used as reference to further characterize the objective tumor response of the measurable dimension of the disease.

All other lesions (or sites of disease) including pathological lymph nodes should be identified as non-target lesions and should also be recorded at baseline. Measurements are not required and these lesions should be followed as “present” or “absent”, or in rare cases “unequivocal progression”.

#### **7.10.3 Evaluation of Target Lesions using RECIST 1.1 Criteria**

**NOTE:** In addition to the information below, also see section 4.3.2 in the international criteria proposed by the Response Evaluation Criteria in Solid Tumors (RECIST) Committee, version 1.1 (Eur J Cancer 45;2009:228-247) for special notes on the assessment of target lesions.

**Complete response (CR)**—Disappearance of all target lesions. Any pathological lymph node (LN) (whether target or non-target) must have decreased in short axis to <10mm.

**Partial response (PR)**—At least a 30% decrease in the sum of the LD of the target lesions taking as reference the baseline sum LD.

**Progressive Disease (PD)**—At least a 20% increase in the sum of the LD of the target lesions taking as reference the smallest sum LD recorded since the treatment started including baseline if that is the smallest on study. In addition to the relative increase of 20%, the sum must also demonstrate an absolute increase of at least 5mm. The appearance of one or more new lesions also constitutes PD.

**Stable disease (SD)**—Neither sufficient shrinkage to qualify for PR nor sufficient increase to qualify for PD taking as references the smallest sum LD since the treatment started.

